9.1.2 Definition of Serious Adverse Event (SAE)

An SAE is defined as “An AE or suspected adverse reaction is considered serious if, in the view of either the investigator or the sponsor, it results in any of the following outcomes:

- Death,
- a life-threatening AE,
- prolongation of existing hospitalization,
- a persistent or significant incapacity or substantial disruption of the ability to conduct normal life functions,
- or a congenital anomaly/birth defect.
- important medical events

Important medical events that may not result in death, be life-threatening, or require hospitalization may be considered serious when, based upon appropriate medical judgment, they may jeopardize the patient or subject and may require medical or surgical intervention to prevent one of the outcomes listed in this definition

“Life-threatening” refers to an AE that at occurrence represents an immediate risk of death to a subject. An event that may cause death if it occurs in a more severe form is not considered life-threatening. Similarly, a hospital admission for an elective procedure is not considered a SAE. All SAEs, as with any AE, will be assessed for severity and relationship to study intervention. All SAEs will be recorded on the appropriate SAE CRF. All SAEs will be followed through resolution or stabilization by a licensed study physician.

9.1.3 Suspected Unexpected Serious Adverse Reactions (SUSAR)

A SUSAR is any SAE where a causal relationship with the study product is at least reasonably possible but is not listed in the Investigator Brochure (IB), and/or Summary of Product Characteristics (SmPC). In the case of Remdesivir medication, particular focus will be directed towards renal function.

9.1.4 Classification of an Adverse Event

The determination of seriousness, severity, and causality will be made by an on-site investigator who is qualified (licensed) to diagnose AE information, provide a medical evaluation of AEs, and classify AEs based upon medical judgment.

9.1.5 Severity of Adverse Events

AEs will be graded according to the following definitions:

- Mild (Grade 1): Events that are usually transient and may require only minimal or no treatment or therapeutic intervention and generally do not interfere with the subject’s usual activities of daily living.
- Moderate (Grade 2): Events that are usually alleviated with additional specific therapeutic intervention. The event interferes with usual activities of daily living, causing discomfort but poses no significant or permanent risk of harm to the research subject.
- Severe (Grade 3): Events interrupt usual activities of daily living, or significantly affects clinical status, or may require intensive therapeutic intervention. Severe events are usually incapacitating.
- Life-threatening (Grade 4): Urgent intervention indicated.

AEs characterized as intermittent require documentation of onset and duration of each episode. The start and stop Duration of each reported AE will be recorded on the appropriate CRF. Changes in the severity of an AE will be documented to allow an assessment of the duration of the event at each level of intensity.

9.1.6 Relationship to Study Intervention

For each reported adverse reaction, the SPONSOR must assess the relationship of the event to the study product using the following guideline:

- Related – The AE is known to occur with the study intervention, there is a reasonable possibility that the study intervention caused the AE, or there is a temporal relationship between the study intervention and event. Reasonable possibility means that there is evidence to suggest a causal relationship between the study intervention and the AE.
- Not Related – There is not a reasonable possibility that the administration of the study intervention caused the event, there is no temporal relationship between the study intervention and event onset, or an alternate etiology has been established.

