2.3 Study design

The NOR-SOLIDARITY study is an adaptive, randomized, open clinical multicentre trial to evaluate the safety and efficacy of possible therapeutic agents in hospitalized adult patients diagnosed with COVID-19. See the WHO COVID-19 core protocol (Appendix 1) for the core trial design. This multicentre add-on trial will follow the WHO core protocol version 10 dated 22.03.2020 but will add additional secondary and exploratory endpoints.

Adults (age ≥ 18 years) recently hospitalized, or already in hospital, with definite COVID and, in the view of the responsible doctor, no contra-indication to any of the study drugs will be randomly allocated between

- Local standard of care alone,
OR local standard of care plus
- Remdesivir (one intravenous loading dose, then daily infusions for altogether 10 days)

The primary objective of the trial is to investigate the effect of Remdesivir on all-cause in-hospital mortality compared to standard of care.

Patients will be followed daily during hospitalization, after 28 days by telephone/sms and then by an outpatient clinical visit after 3 months.

In the core protocol follow-up data are only collected at discharge. In this protocol subjects will additionally be assessed for efficacy and safety both during hospitalization and after hospitalization.

In addition to the global independent data and safety monitoring board (DSMB) as described in the core protocol, a national DSMB will monitor the safety and risk-benefit of the trial interventions in the Norwegian population.

[figure not shown]

Figure 2: The Investigational NOR-SOLIDARITY protocol

3 Objectives and endpoints

Objectives	Endpoints (Outcome measures)
Primary (in line with WHO core protocol)	
To investigate the effect of Remdesivir on all-cause in-hospital mortality compared to standard care.	All-cause in-hospital mortality
Secondary (in line with WHO core protocol)	
Assess the effect of Remdesivir on hospital duration, receipt of ventilation or intensive care, and to identify any serious adverse reactions.	During hospitalization 
 • Receipt of mechanical ventilation • Time to first receiving and duration of mechanical ventilation • Receipt of intensive care • Duration of intensive care • Occurrence of Suspected Unexpected Serious Adverse Reactions (SUSARs)
Secondary (as addition to the WHO core protocol)	

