It is important that data generated now are not destroyed unnecessarily, since they will be of considerable potential value to future generations faced with similar outbreaks of infectious disease. Electronic data and electronic copies of paper documents will be stored for at least 15 years.

9 Safety monitoring and reporting

The PI is responsible for the detection and documentation of events meeting the criteria and definition of an adverse event (AE) and a serious adverse event (SAE). The sponsor is responsible for assessing whether a SAE is defined as SUSAR as well as for reporting of all SUSARs to the national competent authority. Each patient will be instructed to contact the investigator immediately should they manifest any signs or symptoms they perceive as serious. Safety analyses will include tabulation of the type and frequency of adverse events. Any serious adverse events will be reported with comprehensive narratives. Any value of safety laboratory parameters outside the expected ranges will be identified. The methods for collection of safety data are described below.

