10.5.3 Safety analyses

Safety endpoints include death through three months, SAEs, discontinuation of study infusions, and severe AEs. These events will be analysed univariately and as a composite endpoint. Time-to-event methods will be used for death and the composite endpoint. Each AE will be counted once for a given participant and graded by severity and relationship to COVID-19 or study intervention. AEs will be coded using the current version of the Medical Dictionary for Regulatory Activities (MedDRA). AEs will be presented by system organ class, duration (in days), start- and stop-date. Adverse events leading to premature discontinuation from the study intervention and serious treatment-emergent AEs should be presented either in a table or a listing.

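### The relatedness categories in Protocol 9.1.6 overlap: an on-treatment event with another established cause is both Related and Not Related, and neither category matches the SUSAR threshold in 9.1.3

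*Protocol*

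**What the plan says.** Section 9.1.6 gives two categories. *Related* applies when the event is a known effect of the intervention, or when "there is a reasonable possibility that the study intervention caused the AE, or there is a temporal relationship between the study intervention and event". *Not Related* applies when there is no reasonable possibility of causation, or when "there is no temporal relationship between the study intervention and event onset, or an alternate etiology has been established". The section does not say which category wins when both apply.

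Section 9.1.3 sets its own causal test for SUSARs: "A SUSAR is any SAE where a causal relationship with the study product is at least reasonably possible". In addition, the event must not be listed in the reference safety information. Timing by itself is not part of that test.

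Three places deal with who judges. Section 9.1.4 says: "The determination of seriousness, severity, and causality will be made by an on-site investigator". Section 9.1.6 says that "the SPONSOR must assess the relationship of the event to the study product using the following guideline". The opening of section 9 says: "The sponsor is responsible for assessing whether a SAE is defined as SUSAR".

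Relatedness is then used in two places. Section 10.5.3 has each AE "graded by severity and relationship to COVID-19 or study intervention", and section 3 lists SUSAR occurrence among the secondary endpoints taken from the WHO core protocol.

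**The concern.** A two-way classification is usable only if each event falls in exactly one class. Here each class can be entered through a single limb, and the two limbs that matter most in this trial, timing and another cause, are often true together. Remdesivir is given over 10 days to inpatients with COVID-19 (section 5.1). Under 9.1.1, a pre-existing condition that worsens is an AE. Under 9.1.2, all SAEs, like any AE, are assessed for relationship. An obvious example is respiratory failure on day 4 that is established as due to COVID-19 pneumonia. The rule gives two opposite answers for it.

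Two things are at stake. First, the relatedness grading in the safety tables could reflect which limb the assessor happened to apply. The trial is open label (9.2 and 10.2.3), so the judgement has no protection from blinding and leans more heavily on the written rule. Second, the sponsor is told to use a guideline for relatedness that differs from the test the sponsor must apply to SUSARs.

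**Working it through.** The plan gives no figure on this point to reproduce. The check is logical.

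**Inputs, all from 9.1.6.** Four yes/no facts about an event: K, known effect of the drug; RP, reasonable possibility of causation; T, temporal relationship; A, another cause established. Four such facts give 2 × 2 × 2 × 2 = 16 combinations.

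**Rules as written.**
- Related = K or RP or T
- Not Related = (not RP) or (not T) or A

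**Results under three readings of Not Related.**

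| Reading of Not Related | Both | Related only | Not Related only | Neither |
|---|---|---|---|---|
| Literal: (not RP) or (not T) or A | 12 | 2 | 2 | 0 |
| Lenient: (not RP and not T) or A | 8 | 6 | 2 | 0 |
| All three required: not RP and not T and A | 1 | 13 | 1 | 1 |

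Each row sums to 16. The day-4 example has T = 1 and A = 1, which covers 4 combinations because K and RP are free. All 4 meet both definitions on the literal reading and again on the lenient one. They leave the overlap only if all three conditions must hold together. The text's *or* does not say that, and even that reading leaves one combination in both categories and one in neither.

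These are counts of logical cases, not frequencies. Some combinations would be rare in practice, such as a known effect with no reasonable possibility of causation.

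**Comparison with 9.1.3.** The causal part of the SUSAR test is RP alone.
- T = 1 and RP = 0 (4 of 16 combinations): 9.1.6 allows Related, but the 9.1.3 test fails.
- A = 1 and RP = 1 (4 of 16 combinations): 9.1.6 allows Not Related, but the 9.1.3 test is met.

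The mismatch therefore runs in both directions, and no section says which rule governs.

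**Assessors.** Section 9.1.4 gives causality to the on-site investigator, and 9.1.6 gives the relationship assessment to the sponsor. The two can stand together as successive steps. What the protocol does not state is which one enters the tabulation in 10.5.3 when they differ.

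**The case against.** The strongest defence is that SUSARs are handled elsewhere. A reader might infer from the overlap that the SUSAR endpoint itself is undetermined. The document does not support that: section 9 names a single decider, the sponsor, and 9.1.3 gives a threshold with no timing-alone limb. The day-4 example is not automatically a SUSAR. This part of the defence stands.

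A reader might also see a contradiction over who assesses causality. Investigator classification, followed by Medical Monitor review (9.1.9) and sponsor assessment, is a coherent sequence. Which assessment is tabulated is often left to the SAP, which is not at hand. This largely stands; what is left is a request for clarity.

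A third tempting step is to put a number of patients on the problem by applying the 26% intensive-care figure in 10.1 to 406 patients per arm (0.26 × 406 = 105.6). That does not work:
- The 26% is a snapshot (70 of 268 patients in intensive care at the time), not a rate of deterioration after randomization.
- Patients already in the ICU are eligible (4.1), and a condition present at screening is not an AE unless it worsens (9.1.1).
- ICU admission is not itself an SAE criterion in 9.1.2.
- The document gives no share of events falling within the treatment course.

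It can also be said that 9.1.6 opens by speaking of adverse reactions, that it calls itself a guideline, that 9.1.4 rests on medical judgement, and that an established alternative cause is a higher bar than a possible one. These points narrow the range of events affected. They do not remove the overlap: the definitions in 9.1.6 are worded for AEs, 9.1.2 sends all SAEs through a relationship assessment, and a guideline that gives opposite answers cannot steer judgement.

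Finally, the safety endpoints named in 10.5.3 (death, SAEs, discontinuation of infusions, severe AEs) do not depend on relatedness. That is correct and limits the consequence.

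**Conclusion.** The rule is wrong as written and should be corrected. An on-treatment event with another established cause meets both categories in 9.1.6, on the literal reading (12 of 16 combinations overlap) and on a lenient one (8 of 16). The rule also departs from the 9.1.3 threshold in both directions.

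The consequence is bounded. It covers inconsistent relatedness coding in the AE and SAE tables, and a sponsor guideline that conflicts with the sponsor's own SUSAR test. No efficacy analysis is touched, and SUSAR status keeps a named decider and a threshold. The number of events affected cannot be derived from the document.

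The conclusion assumes that *or* in 9.1.6 means what it says and that no precedence rule exists in the site reporting guidelines (9.1.8) or the WHO procedures, neither of which is at hand. Because a definition applied during the trial is stated inconsistently in the protocol itself, a later analysis plan would not by itself repair coding already done.

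**What to change.** Reword 9.1.6 so that the two categories are complementary and use the 9.1.3 threshold:

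- *Related*: there is a reasonable possibility that the study drug caused the event, judged by weighing timing, known drug effects and alternative causes together. Timing alone is not sufficient.
- *Not Related*: there is no such reasonable possibility. An alternative cause is weighed but is not decisive by itself.

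Every event then falls in exactly one category, and the causal part of the SUSAR test is the same judgement.

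Reconcile 9.1.4 with 9.1.6 by stating that the investigator and the sponsor each record an assessment, and which of the two is tabulated under 10.5.3. The sponsor's role in deciding SUSAR status under section 9 can stay as it is. A rule that either party's positive judgement is enough would be a policy choice beyond what the document supports, and this correction does not need it.

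The cost is a wording change in two sections and any matching eCRF guidance. The drawback is that events already classified must be rechecked against the new wording, and some may change category.

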9.1.7 Time Period and Frequency for Event Assessment and Follow-Up

For this study, all Grade 3 and 4 AEs, Grade 1 and 2 AEs for Remdesivir occurring while administration or within the first hour and all SAEs occurring from the time the informed consent is signed through three months follow-up will be documented, recorded, and reported.

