Assess the effect of Remdesivir on 28 days mortality, viral clearance, kidney and myocardial failure, co-infections, organ dysfunction and health-related Quality of Life.	Assessed during hospitalization 
 • Viral clearance as assessed by SARS-CoV-2 PCR in oropharyngeal specimens during hospitalization • Occurrence of kidney failure (eGFR <40 mL/min) • Occurrence of myocardial involvement assessed by biochemical markers as well as echocardiography measuring left ventricular ejection fraction within the first week • Occurrence of co-infections (super infections with bacteria, fungi and other virus) Assessed after 28 days 
 • Overall survival • Patient reported respiratory health status by CAT (Chronic Obstructive Pulmonary Disease (COPD) assessment Test) score Assessed after 3 months 
 • Occurrence of systolic and diastolic cardiac dysfunction and level of remodelling assessed by echocardiography and biochemical markers • Occurrence of pulmonary dysfunction and level of fibrosis assessed by spirometry and thoracic CT scan • Health related quality of life assessed by the RAND 36-item Short Form Health Survey (SF-36) item scores and the 5-dimension EuroQol (EQ-5D) questionnaires index value.
Exploratory (as addition to the WHO protocol)	

Assess the effect of Remdesivir on biomarkers and its safety.	Biomarkers during hospitalization and after 3 months 
 • Inflammatory and anti-inflammatory mediators as assessed in serum and plasma • Markers of extracellular matrix remodelling • Markers of endothelial activation • Markers of platelet activation • Cellular immunity • Prognostic biosignatures (RNA) • Gut microbiota assessed by rectal swab • Pharmacokinetics during hospitalization • Adverse events during hospitalization
---	--

4 Study population

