9.1 Adverse Events and Serious Adverse Events

9.1.1 Definition of Adverse Event (AE)

AE means any untoward medical occurrence associated with the use of an intervention in humans, whether or not considered intervention related. An AE can therefore be any unfavorable and unintended sign (including an abnormal laboratory finding), symptom, or disease temporally associated with the use of medicinal (investigational) product.

Any medical condition that is present at the time that the subject is screened will be considered as baseline and not reported as an AE. However, if the severity of any pre-existing medical condition increases, it should be recorded as an AE.

Given the nature of severity of the underlying illness, subjects will have many symptoms and abnormalities in vitals and laboratory. All Grade 3 AEs will be captured as AEs in this trial and will be considered as notable events. For Remdesivir, additional information on AE grade 1 or 2 occurring while administration or within the first hour will be reported in the eCRF in a separate form; *Remdesivir, mild adverse reaction (grade 1 & 2)*.

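### The adverse event endpoint stops at discharge, which treatment may shift, and grade 1–2 events recorded only around Remdesivir infusions are not kept out of the AE tables

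*Protocol*

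**What the plan says.** **Window.** The objectives table in section 3 gives the exploratory AE endpoint as "Adverse events during hospitalization". Section 9.1.7 sets a longer collection period: grade 3 and 4 AEs, the Remdesivir infusion-period events and SAEs "occurring from the time the informed consent is signed through three months follow-up will be documented, recorded, and reported". Section 10.5.3 names death, SAEs, discontinuation of infusions and severe AEs as safety endpoints, and attaches a period (three months) to death only.

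**Grade.** Section 9.1.1 states "All Grade 3 AEs will be captured as AEs in this trial"; section 9.1.7 adds grade 4. For one arm there is a further rule, to record "Grade 1 and 2 AEs for Remdesivir occurring while administration or within the first hour". Section 9.1.1 says this additional information "will be reported in the eCRF in a separate form", reserved for mild reactions to Remdesivir.

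**Tables.** Section 9 says "Safety analyses will include tabulation of the type and frequency of adverse events". Section 10.5.3 says "Each AE will be counted once for a given participant and graded by severity and relationship to COVID-19 or study intervention" and presents AEs by system organ class. Neither section limits these tables to events collected alike in both arms.

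**The concern.** The stated purpose of the AE endpoint is to assess the effect of Remdesivir on safety, which calls for a comparison between arms.

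First, the endpoint ends at discharge. Discharge happens after randomisation, in an open-label trial, and the protocol itself lists hospital duration among the outcomes treatment may change. If stays differ, two arms with the same daily risk of an AE will show different proportions of patients with an AE. Longer stays under Remdesivir would make it look harmful; shorter stays would make it look protective. Events after discharge are collected but fall outside the stated endpoint.

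Second, a standard-of-care patient has no study infusion, so the infusion-period grade 1–2 count there is zero by construction. If those events enter an any-grade table, background symptoms that happen to fall in an infusion window count against Remdesivir alone. Section 9.1.6 sharpens this: a temporal relationship is enough to class an event as related, and an event during an infusion has one almost automatically.

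**Working it through.** The protocol gives no AE rates and no expected length of stay by arm. Every rate below is an assumption, used to show scale.

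**Denominator.** The arm size of 406 comes from section 10.1 (26% versus 16% in intensive care, two-sided 2.5%, 90% power). It reproduces with the unpooled formula: (2.2414 + 1.2816)² × (0.26×0.74 + 0.16×0.84) / 0.10² = 12.41 × 32.68 = 405.6, so 406. It is not in dispute.

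**1. Window.** Assume a harmless drug and the same AE hazard of 2% per day in both arms. The proportion with at least one in-hospital AE after a stay of *d* days is 1 − 0.98^d.

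- 10 days: 18.3%; 7 days: 13.2%; 5 days: 9.6%.
- Remdesivir 10 days, control 7: 18.3/13.2 = 1.39.
- Remdesivir 10 days, control 5: 18.3/9.6 = 1.90.
- Remdesivir 7 days, control 10: 13.2/18.3 = 0.72.
- Equal stays: 1.0.

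A constant hazard gives a patient well enough to go home the same daily risk as a sick one, so these ratios probably overstate the effect.

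**2. Grade.** Section 5.1 gives ten daily infusions of 30 minutes to 2 hours. Adding the first hour after each, the Remdesivir-only windows total 10 × 1.5 h to 10 × 3 h = 15 to 30 hours, or 6% to 12.5% of ten days. With an assumed background grade 1–2 rate λ per patient-day, the share of patients with at least one chance event in these windows is b = 1 − exp(−λ × hours/24):

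- λ = 0.05 and 15 h: 3.1%.
- λ = 0.2 and 30 h: 22.1%.

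Let g be the share with a grade 3 or higher AE, equal in both arms, and treat the two event types as independent. If the forms are pooled, the any-AE share is g under standard of care and g + (1 − g)b under Remdesivir. The chance of a significant difference (two-sided 5%, pooled null variance, 406 per arm) for a harmless drug is:

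| g (control) | b = 2% | b = 5% | b = 10% |
|---|---|---|---|
| 10% | 11.8%; chance 13% | 14.5%; chance 50% | 19.0%; chance 96% |
| 20% | 21.6%; chance 9% | 24.0%; chance 28% | 28.0%; chance 76% |
| 30% | 31.4%; chance 7% | 33.5%; chance 19% | 37.0%; chance 56% |

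The first figure in each cell is the Remdesivir any-AE share. Check of one cell (g = 10%, b = 5%): the difference is 0.045, the null standard error is √(2 × 0.1225 × 0.8775/406) = 0.0230, and 1.96 × 0.0230 = 0.045, so the chance is about one half.

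If the mild-reaction form stays out of the between-arm table, b = 0: the expected difference is 0 and the false-signal rate is 5%.

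**The case against.** **The mild events are already set apart.** They go on a separate form as additional information, and they are not among the safety endpoints named in 10.5.3. This stands in part. The grade problem is conditional: it arises only if the form is pooled into between-arm tables, which the protocol neither says nor rules out. A reader might infer that the planned tables will show excess harm even for a harmless drug. The text does not support that, because SAEs, severe AEs and death are untouched by the rule. Real infusion reactions are also genuine drug effects; only background events in the infusion windows would be spurious. A count such as 20 to 81 patients (5% to 20% of 406, assumed) does not separate the two.

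**The windows do not contradict each other.** An in-hospital endpoint can be a subset of data collected to three months. This stands: it is a mismatch, not a contradiction. It does not remove the problem that the chosen subset ends at an event treatment may influence.

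**Time at risk is not longer under Remdesivir by design.** A reader might infer this from the ten-day intravenous schedule in 5.1. No section requires a stay until day 10, section 9.4 leaves stopping study medication to the local doctor, and an effective drug could shorten the stay. The direction of any bias is therefore unknown.

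**Table content belongs in the SAP.** Section 10.4 does defer analysis detail, and the choice of grades per table could be settled there. The endpoint window cannot be set aside this way, because section 3 already fixes it.

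**Conclusion.** The point holds in two parts of unequal weight.

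The main part is the window. The AE endpoint in section 3 ends at discharge, so the in-hospital AE proportion is confounded with length of stay, with bias possible in either direction. A period common to both arms is available from data that 9.1.7 already collects.

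The second part is conditional. Grade 1–2 events are recorded in one arm only, and sections 9 and 10.5.3 do not exclude them from the AE tables. Pooling them would add about 1.4 points (g = 30%, b = 2%) to 9 points (g = 10%, b = 10%) to the Remdesivir any-AE share for a harmless drug.

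All these sizes, including the ratios 1.39, 1.90 and 0.72, rest on assumed stays, hazards and event rates. They show that the issue can matter; they are not estimates for this trial. The primary endpoint is not affected. The wording should be corrected before the safety analysis.

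**What to change.** - **Section 3:** replace the in-hospital AE endpoint with grade 3–4 AEs and SAEs over one fixed period from randomisation, the same in both arms, for example to day 28 and to three months. In-hospital AEs can still be described.
- **Section 10.5.3:** state the same period for SAEs and severe AEs, and state that between-arm AE comparisons use only grade 3–4 AEs and SAEs, which are collected alike in both arms.
- **Sections 9 and 10.5.3:** state that the Remdesivir mild-reaction form is reported descriptively for the Remdesivir arm only and enters no between-arm table.
- **SAP:** carry the same wording.

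The cost is wording only. No new data are needed, because collection to three months is already planned and section 2.3 provides a day-28 telephone or SMS contact and a three-month clinic visit. The drawback is that AEs after discharge rest partly on patient report, in an open-label trial.
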